11.2.6 Reporting

11.2.6.1 Serious Adverse Events

The investigator or designee must report all SAEs promptly to Premier Research within 24 hours of first becoming aware of the event by e.g., completing, signing and dating the Serious Adverse Event Report Form, verifying the accuracy of the information recorded in the form with the source documents and eCRF, and sending the SAE form to the Premier Research by one of the following methods:

Email: [contact]

Email: [contact]

[contact]

[contact]

This written report should be submitted on the SAE form provided for this purpose. At the time of first notification, the investigator or designee should provide the following information, if available:

- Protocol number
- Reporter (study site and investigator)
- Suspect IP
- Subject's study number
- Subject's year of birth
- Subject's gender
- Date of first dose of IP(s)
- Date of last dose of IP(s), if applicable
- Adverse event term
- Date of occurrence of the event
- A brief description of the event, outcome to date, and any actions taken
- The seriousness criteria(on) that were met
- Concomitant medication at onset of the event
- Relevant medical history information
- Relevant laboratory test findings
- Investigator's opinion of the relationship to IP(s) ("Is there a reasonable possibility that the IP caused the SAE? Yes or No?")
- Whether and when the investigator was unblinded as to the subject's treatment assignment

Any missing or additional relevant follow-up information concerning the SAE should be sent to the sponsor/sponsor representative via the same contact details above as soon as possible on a follow-up SAE Report Form, together with the following minimal information (initial report, adverse event, date of occurrence, subject identification (ID), study ID, IP, and site number); this will allow the follow-up information to be linked to the initial SAE report.

Specific information may be requested by the Premier Research Pharmacovigilance Department using a follow-up request form or via email communication.

The investigator is required to comply with applicable regulations (including local laws and guidances) regarding the notification of his or her health authorities, institutional review board (IRB)/independent ethics committee (IEC), principal and coordinating investigators, study investigators, and institutions. Each investigator is obligated to learn about the reporting requirements for investigators in his/her country. The study monitor may be able to assist with this.

11.2.6.2 Adverse Drug Reactions

All ADRs should be reported by the investigator in the eCRF.

Suspected serious ADRs must be reported to the sponsor immediately, regardless of the time elapsed since the end of the observation period.

11.2.6.3 Nonserious Adverse Events

Nonserious AEs will be recorded in the eCRF and reported by Premier Research to Mayne Pharma LLC in aggregate monthly status reports.

11.3. Special Considerations

11.3.1 Adverse Events of Special Interest

Since topical retinoids are associated with local application site AEs, particularly when beginning treatment, these events will be followed closely during the study and considered AEs of special interest (AESIs).

11.3.2 Pregnancy

All WOCBP who participate in the study should be counseled on the need to practice highly effective birth control and on the importance of avoiding pregnancy during study participation. Women should be instructed to contact the investigator or study staff immediately if pregnancy occurs or is suspected.

Pregnancy testing will be conducted prior to administration of the IP on every woman of childbearing potential. A woman who is found to be pregnant at the Screening Visit will be excluded from the study and considered to be a screening failure.

A woman who becomes pregnant during IP treatment will be immediately discontinued from study treatment. The investigator must report the pregnancy of any woman who becomes pregnant during or within 30 days after discontinuing treatment as if it were an SAE within 24 hours of learning of the pregnancy, to Premier Research Pharmacovigilance using the Pregnancy Data Collection Form via the same fax number and/or email address as for SAE reporting. If a partner

of a male study subject becomes pregnant, the investigator must report the pregnancy as soon as possible after learning of it to the Premier Research Pharmacovigilance using the Pregnancy Data Collection Form. A separate pregnant partner ICF will be required.

Early Termination Visit assessments are required as soon as possible after learning of the pregnancy in a study subject. The investigator is also responsible for following the pregnancy until delivery or termination. These findings must be reported on the Pregnancy Data Collection Form and forwarded to Premier Research Pharmacovigilance. The event meets the SAE criterion only if it results in a spontaneous abortion or a congenital anomaly. In such case, an additional form (Serious Adverse Event Report Form) must be filled out by the investigator and provided to Premier Research Pharmacovigilance within 24 hours of knowledge of the pregnancy's serious outcome.

Among the clinical studies, 12 pregnancies were reported: 4 resulted in normal births; 5 resulted in spontaneous abortions (none of which was considered related to CD5789); 1 was electively aborted, and 2 were lost to follow-up (IB for CD5789 Cutaneous Formulation).

13. STATISTICS

13.1. Statistical Analysis

This section presents a summary of the planned statistical analyses. A SAP that describes the details of the analyses to be conducted will be written prior to database lock.

Unless otherwise indicated, all testing of statistical significance will be two-sided, and a difference resulting in a P value of ≤ 0.05 will be considered statistically significant.

Summary statistics will be provided for the variables described below. For continuous variables, these statistics will include the number of subjects, mean, standard deviation (SD), median, minimum, and maximum. For categorical variables, these statistics will include the number and percentage of subjects in each category.

The primary analysis period is the first 90 days of treatment (i.e., the Double-blind Period). Overall unblinding will take place at the end of the Double-blind Period of the study only after the database is locked. A second analysis will take place for endpoints assessed from Day 90 through the OLE

Period. The baseline for the safety and efficacy parameters will be measured at Visit 1 or Visit 2, per the Schedule of Events for both the Double-blind Period ([Table 2-1](#)) and OLE ([Table 2-2](#)).

13.1.1 Analysis Populations

The following 5 analysis populations are planned for the Double-blind Period of this study:

- Safety: all subjects who are randomized to treatment and receive at least 1 application of study drug in the Double-blind Period. This population will be the primary population for analyses of safety.
- Intent-to-treat (ITT): all randomized subjects. This population will be used as the primary population for the analysis of efficacy for the Double-blind Period of the study.
- Modified intent-to-treat (mITT): all subjects in the safety population with at least 1 postbaseline assessment of efficacy in the Double-blind Period.
- Per-protocol (PP): subjects in the mITT Population who met all inclusion criteria and no exclusion criteria, were compliant with study drug application, and who had no significant protocol deviations.
- Pharmacokinetic: all subjects in the Safety Population who have at least 1 plasma sample with quantifiable concentration. This population will be used to summarize all PK endpoints.

The following analysis populations are planned for the OLE of this study:

- OLE Safety: all subjects who complete the 90-day Double-blind Treatment Period and receive at least 1 application of study drug in the OLE.
- OLE ITT: all subjects who complete the 90-day Double-blind Treatment Period and sign the OLE informed consent.
- OLE mITT: all subjects in the OLE safety population with at least 1 assessment of efficacy after Visit 6.
- OLE PP: all subjects in the OLE mITT population who met all inclusion criteria and no exclusion criteria, were compliant with study drug application from baseline through EOT, and who had no significant protocol deviations throughout the study.

Inclusion in the analysis populations will be determined prior to database lock. Deviations related to COVID-19 will also be evaluated in determining PP population eligibility.

If a subject is randomized incorrectly or is administered the incorrect IP, analyses of the ITT and mITT populations will be based on the assigned treatment whereas all other analyses will be based on the actual treatment received.

13.1.2 Study Subjects and Demographics

13.1.2.1 Disposition and Withdrawals

For the Double-blind Period, the numbers of subjects randomized, completing Day 90 of the study, and withdrawing early from the Double-blind Period, along with reasons for withdrawal, will be tabulated overall and by randomized treatment group. The number of subjects in each analysis

population will be reported. The number of subjects completing study milestones will also be tabulated by randomized treatment group. This analysis will be conducted for the ITT population.

For the OLE, the number of subjects entering the OLE, completing the study, and withdrawing early, along with reasons for withdrawal, will be tabulated overall. The number of subjects in each analysis population will be reported. The number of subjects completing study milestones will also be tabulated. This analysis will be conducted for the OLE ITT population.

13.1.2.2 Protocol Deviations

A protocol deviation is any noncompliance with the clinical study protocol or International Council for Harmonisation of Technical Requirements for Pharmaceuticals for Human Use (ICH) Good Clinical Practice (GCP) requirements. The noncompliance may be either on the part of the participant, the investigator, or the study site staff. As a result of deviations, corrective actions are to be developed by the site and implemented promptly.

It is the responsibility of the site investigator to use continuous vigilance to identify and report deviations promptly. All deviations must be addressed in study source documents, and reported to Premier Research or Mayne Pharma LLC. Protocol deviations must be sent to the reviewing IRB per their policies. The site investigator is responsible for knowing and adhering to the reviewing IRB requirements. Further details about the handling of protocol deviations will be included in the protocol deviation guidance plan.

Subjects who taper to once-weekly application or who take a “drug holiday” will not be reported as having deviated from the protocol.

13.1.2.3 Demographics and Other Baseline Characteristics

These analyses will be conducted for the ITT and OLE ITT populations.

Demographic variables will include age, sex, race, ethnicity, height, weight, and BMI. Baseline subject characteristics will include medical history, physical examination findings, and IGA score.

Prior and concomitant medications will be summarized by randomized treatment group, by the number and percentage of subjects taking each medication, and classified using World Health Organization Drug Dictionary (WHO-DD) Anatomical Therapeutic Chemical (ATC) classes and preferred terms.

13.1.3 Exposure and Compliance

Investigational product administration will be summarized in terms of each subject’s dose, and in terms of duration of exposure for each period. Descriptive statistics for these quantities, including the mean, median, SD, minimum, maximum, and quartiles, will be provided by treatment group. Additionally, the number of subjects who are compliant with investigational product will be presented by treatment group for the Double-blind Period and overall for the OLE.

Subjects who taper to once-weekly application or who take a “drug holiday” will not be reported as having deviated from the protocol.

13.1.4 Efficacy Analysis

The ITT population will be used as the primary population for the primary analysis of efficacy at Day 90. Select efficacy analyses will be repeated as secondary analyses in the ITT and PP populations for the Double-blind Period. Efficacy analyses will also be repeated in the OLE using the OLE ITT, OLE mITT, and OLE PP populations. No formal inferential analyses will be conducted for efficacy variables in the OLE.

Efficacy endpoints will be based on investigator assessment.

13.1.4.1 Efficacy Endpoints

Primary efficacy endpoint: The proportion of subjects in each treatment group who experience successful resolution of LI where “success” is defined as clear/almost clear overall and at least a 2-grade change from Baseline at Day 90/EOT in the Double-blind Period on the 5-point IGA scale.

Secondary: The secondary endpoints are as follow:

- The difference in mean scores between the active trifarotene cream HE1 and vehicle groups in the following assessment indices from Baseline through Day 90:
 - 5-point VIIS scale for scaling
 - Individual score for roughness (Scale: 0–4)
 - Palm/sole Assessment (Scale: 0–4)
 - Quality of life per DLQI
- The difference in proportion of subjects with presence of fissures on palm/soles (presence/absence, number of fissures, and pain associated with fissures [on a 0-3 scale]) at Day 90 between the active trifarotene cream HE1 and vehicle groups

Exploratory: The exploratory endpoints are as follow:

- The difference in mean ectropion scores (ESS of 0–8) between the active trifarotene cream HE1 and vehicle groups from Baseline through Day 90
- The difference in quality of life per EQ-5D-5L scores between the active trifarotene cream HE1 and vehicle groups from Baseline through Day 90

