	
were compliant with study drug application, and who had no significant protocol deviations.
 
The PK population includes all subjects in the Safety Population who have at least 1 plasma sample with quantifiable concentration. The PK population will be used to summarize all PK endpoints.
 
The following populations are planned for the OLE of this study:
 
The OLE Safety population: all subjects who complete the 90-day Double-blind Treatment Period and receive at least 1 application of study drug in the OLE.
 
OLE ITT population: all subjects who complete the 90-day Double-blind Period and who sign the OLE informed consent.
 
The OLE mITT population: all subjects in the OLE safety population with at least 1 assessment of efficacy after Visit 6.
 
The OLE PP population: all subjects in the OLE mITT population who met all inclusion criteria and no exclusion criteria, were compliant with study drug application from baseline through EOT, and who had no significant protocol deviations throughout the study.
 
Subject Characteristics and Disposition: Descriptive statistics will be used to summarize demographic characteristics (age, sex, ethnicity, and race) and baseline characteristics for all enrolled subjects. Medical history, physical examination findings, and vital sign measurements for all randomized subjects will be presented in listings.
 
Efficacy Analyses: The number and proportion of subjects in each treatment group with successful resolution of LI by Day 90/EOT in the Double-blind Period will be presented. The primary efficacy endpoint will be analyzed using a logistic regression model with treatment and age group as factors. Other baseline characteristics and interactions may be included. The odds ratios and 95% CIs for the odds ratios will be presented. The difference in proportions between the active trifarotene cream HEI and vehicle cream groups, 95% CIs for the differences, and P-values for the differences in treatment will also be presented.
 
The IGA scores as well as secondary and exploratory efficacy endpoints will be analyzed by visit using descriptive statistics through Day 180 (end of OLE treatment period). Change from Baseline through Day 90 will be presented and analyzed using a mixed model for repeated measures (MMRM). The model will include the change from Baseline score as the dependent variable, treatment group as a fixed effect, subject as a random effect, and Baseline score value as a covariate. Frequencies of results and 95% confidence intervals will also be reported, and scores will be analyzed as categorical variables using the Cochran-Mantel-Haenszel test. For subjects who report having fissures, the number of fissures and pain related to fissures will also be presented on a scale of 0-3 (none, mild, moderate, severe).
 
Clinical Pharmacology Analyses: Noncompartmental PK analysis will be performed for the PK subset of subjects, as data permit. Plasma concentrations of CD5789 and its major metabolites will be measured and will be listed by subject.
 
Safety Analyses: Safety and tolerability will be assessed based on the incidence of reported TEAEs, and SAEs, including relationship to study drug and severity, as well as physical examination findings, vital sign measurements (supine systolic blood pressure [SBP] and diastolic blood pressure [DBP] and pulse), clinical laboratory results (hematology, including serum aminotransferases and serum lipids, coagulation, clinical chemistry, and urinalysis) and 12-lead ECGs. Descriptive statistics for observed values and change from Baseline will be calculated at each visit within each study period and by treatment group within cohort.

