8.2. Study Entry Criteria

8.2.1 Inclusion Criteria

A subject will be eligible for study participation if he or she meets all of the following criteria:

1. Subject is ≥ 18 years old.
2. Subject has known diagnosis of LI.
3. Subject has moderate to severe (IGA 3–4) LI on the IGA of LI severity.
4. Subject has signed an ICF at Screening before any investigational procedures.
5. Subject who is participating in optional photography has signed a photography ICF.
6. Subject who is participating in the optional PK substudy has signed a PK ICF.
7. Subject is not of childbearing potential, i.e., a female who is postmenopausal (absence of menstrual bleeding for 1 year before Baseline, without any other medical reason), or has documented hysterectomy, bilateral salpingectomy, or bilateral oophorectomy). For individuals with permanent infertility due to an alternate medical cause other than the above, (e.g., Mullerian agenesis, androgen insensitivity), investigator discretion should be applied to determining study entry.

OR

Subject is a woman of childbearing potential (WOCBP) or a male subject with sexual partners capable of reproduction who agrees to use 2 effective forms of contraception during the study and for at least 1 month after the last study drug application. The 2 authorized forms of contraception are condom used with 1 of the following methods of contraception:

- bilateral tubal ligation

- combined oral contraceptives (estrogens and progesterone), vaginal ring, or implanted or injectable hormonal contraceptives with a stable dose for at least 1 month before Baseline; hormonal contraceptives must inhibit ovulation
- intrauterine device (IUD) inserted at least 1 month before Baseline

OR

Agrees to abstain from heterosexual intercourse during study participation and for 1 month after the last application of study drug and to use a highly effective contraceptive as backup if he or she becomes sexually active during the study. Abstinence is only acceptable if this is the subject's usual lifestyle. Periodic abstinence (calendar, symptothermal, postovulation methods), withdrawal (coitus interruptus), spermicides only, and lactational amenorrhoea method are not acceptable methods of contraception.

AND

Male subjects may not donate sperm during the study and for at least 1 month after the last study drug application.

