10.2.2.1 Baseline Visit (Visit 2, Day 1)

The following procedures will be performed on Day 1 in the study clinic:

1. Review inclusion/exclusion criteria.
2. Record responses to DLQI and EQ-5D Quality of Life Questionnaires.
3. Perform a limited physical examination.
4. Record vital signs (blood pressure and pulse).
5. Record concomitant medications and concomitant therapies.
6. Record IGA.
7. Record VIIS.
8. Record roughness assessment.
9. Record palm/sole assessment.
10. Record palm/sole assessment of fissuring.
11. Record ectropion score.
12. At sites where the photographic substudy is conducted, take photographs of subjects who have provided informed consent for the photography.
13. Perform a 12-lead ECG.
14. Perform urine pregnancy test for WOCBP.
15. Collect blood and urine for routine laboratory tests (subject must be fasting; i.e., at least 8 hours) and coagulation panel.
16. Randomize via IWRS.
17. Collect a predose PK blood sample (all subjects).
18. Among subjects who consent to participate in the PK substudy, ensure that PK lines are placed before IP application. The IP will be applied in the clinic at this visit, and samples for PK will be taken at 1, 2, 4, 8, 12, and 24 hours postdose on Day 1.
19. Among subjects in the PK study, perform additional ECGs at times of serial sampling.

20. Clinic staff instructs subject on study drug application, applies initial study drug dose and measures amount used (i.e., study staff will weigh kits (tubes and boxes, but not leaflets) before and after the first application. If the product will be applied at home by someone other than the study subject, it is recommended that this person assist with application at this visit to learn how the IP is applied.
21. Assess and record local tolerance/AEs.
22. Dispense study drug and diaries.
23. Advise subjects regarding permitted emollient(s) for use on nontreatment days; use of emollient(s) and/or sunscreen on study drug treatment days within 4 hours before or after study drug application is prohibited. Remind subjects that at least 24 hours must have elapsed since IP application before their next visit. Subjects should not to apply IP on visit days until after the visit.

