10.3.1.1 Investigator's Global Assessment

The primary endpoint is the number of subjects in each treatment group who experience successful resolution of LI where "success" is defined as clear/almost clear and at least a 2-grade change from Baseline at Day 90/EOT in the Double-blind Period on a 5-point IGA full body scale.

The investigator will rate the subject's condition using the 5-point IGA at each time point shown in the Schedule of Events (Section 2.2).

The IGA will be measured on a 5-point scale, excluding the following areas: knees, elbows, neck, palms, soles, axillae, groin, and scalp:

0	Clear	No scaling and no roughness
1	Almost Clear	Occasional fine scales; hardly palpable roughness (mostly smooth)
2	Mild	Small and fine scales predominate; no more than a few large scales; mild roughness on palpation
3	Moderate	Some large scales that may be thick; coarse roughness on palpation
4	Severe	Confluent, primarily large (>1 cm), thick scales with plate-like hyperkeratosis

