10.3.1.4 Palm/Sole Assessment

Thickening of the skin on the palms and soles will be measured on a 5-point scale.

0	Clear	No thickening, no roughness, no fissure
1	Almost Clear	Only slight thickening, minimal to no roughness, no fissures
2	Mild	Some thickening, mild roughness on palpation, few fissures may be present
3	Moderate	Substantial and diffuse thickening, coarse roughness on palpation may be present, fissures may be present
4	Severe	Very thickened and rough skin, numerous fissures

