13.1.4.3 Secondary Analyses

Secondary and exploratory efficacy endpoints will be analyzed separately for each period (Double-blind and OLE) using descriptive statistics.

Additionally, for the Double-blind Period only, change from Baseline in continuous secondary endpoints through Day 90 will be presented and analyzed using a mixed model for repeated measures (MMRM). The model will include the change from baseline score as the dependent variable, treatment group as a fixed effect, subject as a random effect, and baseline score value as a covariate.

For subjects who report having fissures, descriptive summaries of the number of fissures and pain related to fissures will also be presented by treatment group and body area for each period.

The DLQI scores will also be analyzed using descriptive statistics through Day 90.

The proportion of subjects with at least a 50% reduction in IGA score from Baseline will be analyzed using the same logistic regression analysis described in Section 13.1.4.2.

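### The fissure endpoint compares presence at Day 90 without using Baseline fissure status: no bias, but a blurred reading and some avoidable loss of precision (minor).

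*Protocol*

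**What the plan says.** The endpoint, in Section 13.1.4.1 and the Synopsis, is "The difference in proportion of subjects with presence of fissures on palm/soles" at Day 90. It is a status at one visit. The mean-score endpoints in the same list are compared "in the following assessment indices from Baseline through Day 90".

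The severity criterion for entry (Section 8.2.1) is "Subject has moderate to severe (IGA 3–4) LI on the IGA of LI severity". Section 10.3.1.1 measures the IGA "excluding the following areas: knees, elbows, neck, palms, soles, axillae, groin, and scalp". No inclusion criterion mentions fissures. On the palm/sole scale (Section 10.3.1.4), grades 0 and 1 have none, grade 2 reads "Some thickening, mild roughness on palpation, few fissures may be present", grade 3 likewise makes them optional, and only grade 4 has them by definition.

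Baseline status is collected: the Visit 2 list (Section 10.2.2.1) includes "Record palm/sole assessment of fissuring".

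On analysis, Section 13.1.4.3 gives descriptive statistics for all secondary endpoints. It puts the Baseline value into a mixed model for continuous secondary endpoints only, and names no test for the fissure proportion. The Synopsis adds that "scores will be analyzed as categorical variables using the Cochran-Mantel-Haenszel test", with no stratification factor. Fissure number and pain are summarised for subjects who report fissures.

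**The concern.** A subject with no fissures at entry already has the favourable result and needs no change to keep it. The Day 90 proportion therefore mixes three things: fissures that cleared, fissures that were never there, and new fissures. A reader of the result cannot tell which of them moved.

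There is also a cost in precision. Variation in Day 90 status that comes only from who had fissures at entry stays in the error term, and with about 32 to 40 subjects per arm a chance imbalance at Baseline carries into the observed difference. The data needed to remove this are already on the case report form.

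**Working it through.** **Plan's own figure.** None exists for this endpoint. The only power statement (Section 13.2) concerns IGA success.

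**Inputs from the Protocol.** 120 subjects randomised 1:1:1, so 40 per arm; 32 evaluable per arm after 20% loss (Section 13.2); two-sided 0.05 (Section 13.1).

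**Inputs assumed, because the Protocol gives none.** b = share with fissures at Baseline, 30% to 90%; q = share of those with fissures at Day 90, 70% to 80% on vehicle v 40% to 50% on active; r = share with new fissures among the rest, 0% to 20%.

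**Share fissure-free with no treatment effect.** This is 1 - [bq + (1 - b)r]. With q = 0.8 and r = 0.1 it is 69%, 55% and 41% for b = 0.3, 0.5 and 0.7. Much of the favourable outcome is present without any drug effect.

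**One case by hand** (40 per arm, b = 0.5, q = 0.8 v 0.5, r = 0.10 v 0.05):
- Vehicle: 0.5 × 0.8 + 0.5 × 0.10 = 0.450. Active: 0.5 × 0.5 + 0.5 × 0.05 = 0.275. Difference 0.175.
- Unstratified: pooled rate 0.3625, variance 0.3625 × 0.6375 = 0.2311, SE = √(0.2311 × 2/40) = 0.1075. Ratio 1.63; power ≈ Φ(1.63 - 1.96) = 37%.
- Stratified: the within-stratum pooled rates are 0.65 and 0.075, with variances 0.2275 and 0.0694 and mean 0.1484. SE = √(0.1484 × 2/40) = 0.0861. Ratio 2.03; power ≈ Φ(0.07) = 53%.

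**Simulation.** 40,000 trials per cell. The pooled two-proportion test is compared with the Cochran-Mantel-Haenszel (CMH) test stratified by Baseline presence. Without strata, the CMH statistic is the Pearson chi-square times (N - 1)/N, so the pooled test is in effect the Synopsis test with no stratum. Entries are unstratified → stratified power in %, with the gain in points from unrounded values.

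| Per arm | q (vehicle v active) | r (vehicle v active) | b = 30% | b = 50% | b = 70% | b = 90% |
|---|---|---|---|---|---|---|
| 40 | 80 v 50 | 10 v 5 | 25→37 (+11) | 37→53 (+16) | 55→67 (+12) | 72→78 (+5) |
| 32 | 80 v 50 | 10 v 5 | 22→30 (+8) | 32→44 (+12) | 47→57 (+10) | 64→68 (+4) |
| 40 | 70 v 40 | 0 v 0 | 19→30 (+11) | 32→48 (+16) | 50→62 (+13) | 71→74 (+3) |
| 32 | 70 v 40 | 10 v 10 | 14→16 (+3) | 25→31 (+6) | 42→47 (+5) | 62→62 (0) |
| 32 | 70 v 50 | 20 v 15 | 13→14 (+1) | 19→21 (+2) | 26→27 (0) | 35→34 (-1) |
| 40 | 80 v 50 | 0 v 0 | 18→33 (+15) | 29→51 (+22) | 49→67 (+17) | 71→78 (+7) |

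The first five rows span about -1 to +16. The last row shows where that range is exceeded: high persistence on vehicle and no new fissures at all. A larger effect (80% v 40%) with few or no new fissures also exceeds it, up to about +25. At the other end, when nearly everyone has fissures at Baseline, or Baseline predicts Day 90 weakly, stratifying gains nothing.

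**Type I error.** With no treatment effect, the stratified test stays at or slightly below 5%, and the unstratified test is at about 5% to 6%.

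**The case against.** The strongest objection is that strata for a secondary test belong in the SAP, which is not at hand, and that CMH is by nature a stratified method. That is fair as far as it goes: nothing in the Protocol forbids a Baseline stratum, and the SAP may set one. But the Protocol itself fixes this endpoint as status at Day 90, and it states Baseline adjustment for the continuous secondary endpoints while stating none here.

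It can also be said that the loss concerns a test that Section 13.1.4.3 does not name, and that the Synopsis sentence speaks of scores. This stands in part. The power figures bear on the Synopsis test if it is applied to fissure presence; the same loss of precision would widen a confidence interval for the difference.

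The palm/sole grade partly covers fissures and does have a Baseline-adjusted analysis. It mixes them with thickening and roughness, so it does not answer the question about fissures.

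A reader might infer that a fixed dozen or more points of power are lost. The documents do not support that: they give no prevalence, persistence or incidence of fissures, and reasonable choices take the figure to zero.

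**Conclusion.** The point holds as a minor one. The endpoint counts never-fissured subjects and resolved subjects alike, and the recorded Baseline status enters no stated analysis of presence. Under the assumptions above, stratifying changes power by about -1 to +16 points in most combinations, and by more only with a strong effect and few or no new fissures.

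Three stronger readings are not supported. The comparison is not biased: randomisation balances Baseline fissures on average, and the unstratified type I error is close to nominal. Nothing in the Protocol shows that Baseline status is the strongest predictor of Day 90 status, plausible as that is. Nor can it be said that the endpoint has little chance of showing an effect: unstratified power runs from low to above 70% in the table, depending on the assumptions, and stratifying does not make a small trial a large one.

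**What to change.** In Section 13.1.4.3, state that presence of fissures at Day 90 will be compared in all randomised subjects with the CMH test and a common risk difference, each active arm against vehicle, stratified by presence of fissures at Visit 2. Add a table by arm of resolution among subjects with fissures at Baseline and of new fissures among those without. Make the Synopsis sentence agree.

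Restricting the analysis to subjects with Baseline fissures is not advised as the main comparison, because it drops the new fissures. The tabulation gives that view without losing anyone.

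The cost is one sentence and one table. No new data are needed, and entry criteria, visits and treatment are unchanged. The only statistical price is the loss of up to about 1 point of power in the least favourable cases above.
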